4.4 Handling of missing safety indicators

The missing values of safety evaluation indicators were filled by the method of Worst Observational Data Carryover (WOCF).

According to the conservative principle, if the severity of an AE is missing, it will be recorded as "grade 3" in the summary description, and if the relationship between an AE and the investigational medical device is missing, it will be recorded as "probable" in the summary description as "probable".

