- (3) The missing values of DCR and primary safety evaluation indicators
 (proportion of CTCAE grade 3 toxicities, proportion of CTCAE grade
 4 and 5 toxicities) at 3 months after the end of treatment can be estimated using worst-case scenarios.
- (4) The missing values of qualitative secondary effectiveness evaluation indicators ORR, DCR and long-term follow-up effectiveness evaluation indicators can be estimated using worst-case scenarios;
- (5) The missing values of quantitative secondary efficacy evaluation indicators DOR, tumor markers, product ease assessment and long-term follow-up effectiveness evaluation indicators were not estimated.
- (6) Erroneous, unreasonable data (out-of-range data and data that contradicts other data or indicators of the study protocol) can be treated as missing values;
- (7) Worst-case estimates are used for missing values for all minor safety indicators;

- (8) The sensitivity analysis of the main effectiveness evaluation indicators and main safety evaluation indicators after treatment was carried out in the whole analysis center.
- (9) The sensitivity analysis of all secondary effectiveness evaluation indicators after treatment was carried out in the whole analysis center.
- (10) For all secondary safety evaluation indicators after treatment, sensitivity analysis was carried out in the security dataset.

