5.5.1 Proportion of CTCAE toxicity

The severity of AEs was assessed according to Common Adverse Event Common Terminology Criteria

Confidential Information Page 13 / 17

Statistical Analysis Plan Version: V1.0 Date: 2022-11-11

(CTCAE) V5.0.

Grade 1: mild, asymptomatic or mildly symptomatic, clinical or diagnostic findings only, no treatment

required;

Level 2: moderate, minimal, localized, or non-invasive interventions, age-related limitations in instrumental

activities of daily living (ADLs) (instrumental ADLs refer to cooking, grocery or clothing shopping, phone access,

financial management, etc.);

Grade 3: severe or medically significant, but not immediately life-threatening, hospitalization or prolonged

hospital stay, disability, restriction of self-care ADL (self-care ADL refers to bathing, dressing and undressing,

eating, toileting, taking medications, not being bedridden);

Grade 4: life-threatening; requiring urgent intervention;

Grade 5: AE-related death.

The number and percentage of subjects who achieved each grade of CTCAE toxicity were calculated, and

the details of toxicity were described in a table.

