5.6 Sensitivity analysis

If the receiver effectiveness index was filled by the worst observational data carry-over (WOCF) method,

the sensitivity analysis of the main effectiveness measure was performed based on FAS. When the conclusions

of FAS and PPS are consistent, the confidence of the test results can be enhanced. When the conclusions of the

two groups are inconsistent, the analysis based on the inclusion of PPS population should be the main one, and

the differences should be fully discussed and explained.

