5.8 Interim analysis

Not applicable.

Confidential Information Page 15 / 17

Statistical Analysis Plan Version: V1.0
Date: 2022-11-11

6 Changes to the protocol analysis plan

Section 8.7.2 of the original protocol provided that the missing value of the safety index was estimated using the worst-case scenario. According to the conservative principle, SAP has made the following conventions: if the severity of an AE is missing, it will be recorded as "level 3" in the summary description, and if the relationship between a TEAE and the investigational medical device is missing, it will be recorded as "probable" related to the investigational medical device in the summary description.

Confidential Information Page 16 / 17

7 Annex

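### The SAP's grade 3 default for ungraded adverse events adds nothing to the zero-tolerance grade 4-5 criterion, and the protocol's main-safety sensitivity analysis is dropped without being declared

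*SAP*

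**What the plan says.** Protocol 4.5 sets two safety criteria on raw counts. The trial fails if the grade 3 proportion exceeds 5%, and it fails if grade 4-5 toxicity occurs at all.

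Protocol 4.7.2 gives the missing-data principles. Item (3) allows worst-case estimation of the primary disease control rate and of both safety proportions, the grade 4-5 one included. Item (8) states: "The sensitivity analysis of the main effectiveness evaluation indicators and main safety evaluation indicators after treatment was carried out in the whole analysis center". Item (10) states: "For all secondary safety evaluation indicators after treatment, sensitivity analysis was carried out in the security dataset".

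SAP 4.4 fills missing safety indicators by worst observation carried forward (WOCF). For an ungraded event it adds: "According to the conservative principle, if the severity of an AE is missing, it will be recorded as" grade 3, for the summary description. SAP 5.5.1 then plans the count: "The number and percentage of subjects who achieved each grade of CTCAE toxicity were calculated". Its own definitions include "Grade 4: life-threatening; requiring urgent intervention" and "Grade 5: AE-related death".

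On sensitivity, SAP 5.6 says that "the sensitivity analysis of the main effectiveness measure was performed based on FAS" and names no safety indicator. SAP 5.5 uses the Safety Set and plans no sensitivity analysis. SAP 6, the section for changes from the protocol, begins: "Section 8.7.2 of the original protocol provided that the missing value of the safety index was estimated using the worst-case scenario". It then states the conventions for missing severity and missing device relationship, and nothing more. The rule it cites stands in section 4.7.2 of the protocol reviewed here.

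**The concern.** There are two separate problems.

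First, the default is presented as conservative, but there are two safety criteria and it is conservative for only one. However many events lack a grade, the default cannot put a subject into the grade 4-5 count, where a single subject is decisive. An ungraded event that was life-threatening or fatal would be counted below the grade that SAP 5.5.1 itself gives it.

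Second, the protocol states the main-safety sensitivity analysis as something to be done, and the SAP does not carry it over. Protocol 4.8 normally limits the report to analyses agreed in the SAP and treats additions as exploratory. An analysis left out of the SAP is therefore likely to be missing from the report or to carry less weight there.

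What is at stake is a pass/fail safety conclusion that turns on one to three subjects.

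**Working it through.** **Inputs.** Planned enrolment is 47 (protocol 4.2.1, SAP 1.4). With a target of 80%, an expected rate of 95% (protocol 3.1.2), two-sided 0.05 and 80% power:

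n = [(1.960·√(0.80·0.20) + 0.842·√(0.95·0.05)) / 0.15]² ≈ 41.6, so 42; then 42/0.90 = 46.7, so 47.

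The plan's figures reproduce. They are sized on disease control, not on safety. Taking 47 as the size of the Safety Set is an assumption.

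**Limits in subjects.** The grade 3 criterion fails when k/47 > 0.05, that is k > 2.35. So 2/47 = 4.3% passes and 3/47 = 6.4% fails. At 41 subjects the limit is 0.05 × 41 = 2.05, with 2/41 = 4.9% and 3/41 = 7.3%, so the same counts apply for every Safety Set size from 41 to 47. The grade 4-5 criterion fails at 1 subject.

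**Effect of the default.** Take one ungraded event that was truly grade 4-5, in a subject with no other grade 3 or higher event. No other subject has grade 4-5. Pass here means that both safety criteria are met.

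| Other grade 3 subjects | Grade 3 proportion under the default | Grade 4-5 count under the default | Result under the default | True result |
|---|---|---|---|---|
| 0 | 1/47 = 2.1% | 0 | pass | fail |
| 1 | 2/47 = 4.3% | 0 | pass | fail |
| 2 | 3/47 = 6.4% | 0 | fail | fail |

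The verdict is wrong in the first two rows. From two other grade 3 subjects upwards, the default fails the trial anyway through the 5% criterion.

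**Does the default govern these counts?** Its wording refers to the summary description. But SAP 5.5.1 counts subjects by grade, and the SAP gives no other rule for an ungraded event. SAP 6 also presents the default next to the protocol's worst-case rule for safety. The natural reading is that it governs, though this is an inference.

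**Sensitivity analysis, side by side.** Protocol 4.7.2(8) covers main effectiveness and main safety. SAP 5.4.1 and 5.6 cover main effectiveness only. SAP 6 is silent on the difference. The population named in item (8) is garbled in translation. It appears to mean the full analysis set (FAS), because item (10) names the safety dataset separately. The omission stands under either reading. Item (10) has no counterpart in the SAP either, but secondary safety carries no pass/fail criterion.

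**What a plain FAS repeat would show.** FAS entry needs one device treatment and one post-baseline observation; Safety Set entry needs one device treatment and one safety assessment (protocol 4.9, SAP 3). The sets are nearly the same, so a repeat on FAS says little about missing data. Scoring subjects who lack the month-3 safety assessment as grade 3 says more. With g observed grade 3 subjects and m such subjects, the limit is crossed when (g + m)/47 > 0.05, so at g + m = 3. That means m = 3, 2 or 1 for g = 0, 1 or 2.

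**The case against.** The strongest reply on the default is that the case is remote. Investigators grade events under CTCAE V5.0, and missing data go to review before analysis (protocol 4.7.2). An event resulting in death is by definition serious and would be listed separately (SAP 5.5.5). SAP 5.5.1 already defines grades 4 and 5, so an adverse-event-related death has a grade by definition. All of this stands as to frequency. It does not settle which rule applies: SAP 4.4 is the only explicit instruction for a missing grade, and read literally it gives grade 3.

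On the sensitivity analysis, the reply is that the protocol's items are basic principles, that detail is left to the SAP, and that a FAS repeat would change little. The last point stands and shapes the fix. It does not excuse an undeclared omission.

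A reader might infer more than the documents support:

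- That the grade 3 convention was slipped in. It was not; SAP 6 declares it. Only the dropped analysis is undeclared.
- That the default is lenient overall. It is strict for the 5% criterion, where three such subjects fail the trial.
- That WOCF breaches the protocol. WOCF cannot create an event that was never observed, but protocol 4.7.2(3) is permissive about worst-case estimation, so there is no breach.
- That the 10% dropout allowance indicates how many safety grades will be missing. Protocol 4.4 defines it as the share of participants who cannot enter the primary analysis, which is a different quantity.

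**Conclusion.** Both points hold and should be corrected. The omission of the main-safety sensitivity analysis is a plain difference between the two documents. The one-sided default rests on reading SAP 4.4 as governing the counts in SAP 5.5.1, which is the only rule the SAP offers.

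The size is conditional. With a Safety Set of 47, and equally from 41 to 47, one truly grade 4-5 event left ungraded changes a fail into a pass when 0 or 1 other subjects have grade 3 toxicity. The documents give no number of ungraded events or of subjects with missing safety data, so this shows what the rule permits and is not a forecast. They do not support a claim that the trial's safety conclusion is wrong or likely to be wrong.

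**What to change.** 1. **SAP 4.4.** Keep grade 3 as the default for an event still ungraded after query, with one exception. An event recorded as leading to death counts as grade 5, and one recorded as life-threatening counts as grade 4, in line with SAP 5.5.1. The death condition should refer to the event leading to death, because a subject's death and an adverse-event-related death are not the same. This assumes that the case report form captures both facts, which should be confirmed.
2. **SAP 5.6.** Restore the main-safety sensitivity analysis of protocol 4.7.2(8), or declare its removal in SAP 6. If it is restored, make it informative with one table. Recount the grade 3 proportion with Safety Set subjects who lack the month-3 safety assessment scored as grade 3. Beside the grade 4-5 result, report the number of such subjects and the number of ungraded events.

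Scoring the missing subjects as grade 4-5 is not worth adding: any one of them fails that criterion, so the result is known in advance.

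The cost is a few lines of wording and one small table. The downside is that the recount may look less favourable than the main safety result. No endpoint or threshold changes.

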4.5 Missing processing of other data

If other data are missing, a footnote will be provided under the statistical analysis table if there is a special note to fill in the summary.

5 Methods of statistical analysis

5.1 Statistical software

Statistical Analysis System (SAS) version 9.4 was used for programmatic analysis.

5.2 General principles

In general, continuous variables will be statistically described using the number of cases, arithmetic mean, standard deviation, median, 25% quantile (Q1), 75% quantile (Q3), minimum and maximum values, etc., while categorical variables will be statistically described using frequency, frequency, incidence, and composition ratio. Unless otherwise specified, all statistical tests will be performed using a two-sided test of α =0.05 to calculate a two-sided 95% confidence interval.

Unless otherwise specified, the following conventions will be followed for the retention of decimal places in this statistical analysis:

Table 3 Data decimal place retention provisions

Statistics	Decimal place provisions
Arithmetic mean, median, Q1, Q3	1 decimal place more than the actual number of decimal places.
standard deviation	1 decimal place more than the arithmetic mean and no more than 4 decimal places.
Minimum, maximum	Same as the actual number of decimal places.
Frequency, incidence, composition ratio	Keep 1 decimal place as a percentage, and the result with a frequency of 0 is "0", and the result is 100% of the display is "100".
Confidence limit	Metrological data: Same as arithmetic mean decimal places

Confidential Information Page 10 / 17

Date: 2022-11-11

	Counting data: 1 decimal place is kept as a percentage.
Test statistics (e.g., chi-square or t-value , etc.).	Keep 4 decimal places.
P-value	Keep 4 decimal places, and if the specific value is less than 0.0001, it will be represented as "<0.0001".

5.3 Subject characteristics

5.3.1 Distribution of participants

The number and percentage of subjects participating in screening, screening success, enrollment, completion of radiotherapy, completion of primary efficacy evaluation, completion of trial and early withdrawal, and each reason for withdrawal will be described throughout the trial.

5.3.2 Deviation from the protocol

Depending on protocol deviations and the specific situation, participants who are not included in FAS, PPS, or SS will be discussed at the data review meeting and identified prior to database locking.

The number, number and incidence of protocol deviations in each category are summarized and the list details the regimen deviations of the subjects.

5.3.3 Demographic characteristics and baseline data

Demographic data and baseline data will be analysed based on FAS. The demographic indicators included gender and age, and the baseline data indicators included height, weight, vital signs, ECOG physical condition classification, and cardiac function classification, and the above indicators were summarized descriptively.

5.3.4 History of tumor treatment

The history of tumor treatment will be analyzed based on SS. Treatment history includes surgical treatment history, radiation therapy history, interventional therapy history, cytotoxic drug treatment history, immunotherapy history, and targeted therapy history, and the above treatment history is summarized descriptively.

5.3.5 History of present tumor presentness

The history of present tumor will be summarized based on FAS. The indicators of present history of tumor include diagnosis basis, tumor type, tumor location, tumor status, pathological classification, and TNM stage. The frequency and composition ratio of the above categorical variables were calculated.

The list details the subject's present medical history.

5.3.6 Past medical history

A detailed description of the subject's past medical history was based on the SS list.

5.3.7 Prior/concomitant medications

Confidential Information Page 11 / 17

Date: 2022-11-11

Prior medication refers to medication taken prior to the first radiation therapy.

Prior/concomitant medications will be summarized based on SS. Prior/concomitant medications were coded

using the World Health Organization Pharmacological Dictionary (WHODD) (version: 09/2021) according to

pharmacology/therapeutics (ATC02).and Preferred Name (PN) classification, and the frequency and percentage

of previous/concomitant medications were counted.

The list details the subject's previous/concomitant medications.

5.3.8 Concomitant therapy

A detailed description of the subject's concomitant treatment based on the FAS list.

5.3.9 Radiation therapy plan

Based on FAS, the radiotherapy plan was described and summarized, including the treatment cycle, the total

dose of the target area of the radiotherapy plan, and the fractional dose. The list describes the radiotherapy plan

design for each subject.

The list describes the dose limits for organs at risk.

To summarize the use of respiratory gating by participants in radiotherapy delivery.

5.4 Effectiveness evaluation indicators

5.4.1 Key Effectiveness Indicators

The primary effectiveness evaluation was based on the Full Analysis Set (FAS) and the Protocol-Consistent

Set (PPS).

The number and percentage of cases that achieved tumor disease control at 3 months during the follow-up

period were calculated, and the 95% confidence interval of tumor disease control rate was calculated by Clopper-

Pearson, and the target value of tumor local control rate was 80%, and if the lower limit of the 95% confidence

interval of the test results was greater than 80%, the tumor local control rate was reached. The single-sample chi-

square test was used to compare whether there was a statistical difference between the local control rate and the

target value.

For the evaluation results of the imaging review team, if the efficacy evaluation results of the two evaluators

are consistent, the final evaluation results of the two evaluators will be taken, and if the evaluation results of the

two evaluations are inconsistent, the independent evaluation value of the third evaluator will be taken as the final

evaluation results.

Based on FAS, the sensitivity analysis of the main effectiveness indicators was carried out, and the missing

values of the main effectiveness evaluation indicators were filled by the method of Worst Observational Data

Confidential Information Page 12 / 17

Statistical Analysis Plan Version: V1.0
Date: 2022-11-11

Carryover (WOCF).

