3.1.4 Effectiveness evaluation methods

If it is not possible to follow up at the clinical trial center according to the visit arrangement due to the epidemic, the clinical examination can be examined by other tertiary hospitals, and the test results will be transmitted back to the clinical trial center for evaluation; The carrier of imaging data in the outer hospital is not limited, and it is necessary to ensure that the imaging department of the center can be opened and read.

3.1.4.1 The main effectiveness evaluation indicators and the methods and time selection of their evaluation, recording and analysis

(1) Tumor disease control rate (DCR).

Reason for selection: According to the clinical trial effectiveness evaluation in the "Guidelines for the Review of Clinical Evaluation Technologies of Proton Carbon Ion Therapy System" (CFDA Circular No. 4 [2018]): "In view of the local characteristics of radiotherapy, it is recommended that the efficacy evaluation should be based on local control, and according to the different diseases, the common standards in clinical research, such as the efficacy evaluation criteria for solid tumors, should be reasonably adopted RECIST. The efficacy evaluation can be divided into complete response CR, partial response PR, disease stable SD, disease progression PD, and the effective definition is: "CR+PR+SD." "; Due to the particularity of the disease, the evaluation method recommended in the relevant diagnosis and treatment guidelines is selected. The tumor disease

control rate was selected as the main effectiveness evaluation index, which was relatively objective and reproducible, and adopted the common standard in clinical research, which was widely recognized and applied by clinicians.

Definition of indicators: the occurrence of CR, PR and SD after the end of treatment is disease control; No biochemical recurrence at the end of prostate cancer treatment, no regional lymph nodes or distant metastases, considered disease control. Proportion of participants who developed disease control three months after the end of the last radiotherapy.

Metric type: Qualitative.

Data collection time: screening period, 3 months \pm 7 days after the end of the last treatment.

Evaluation time: 3 months \pm 7 days after the end of the last treatment.

Site of evaluation: Tumor receiving radiation therapy.

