Evaluation method: The changes in tumor CT or MRI imaging before and after treatment were evaluated by an independent imaging review panel according to RECIST 1.1. At 3 months of radiographic evaluation, if PD is found, PET-CT is required to confirm it.

Calculation formula: DCR = number of disease control subjects / total number of subjects × 100%.

Criteria: See RECIST 1.1 for details. At the time of 3-month imaging evaluation, if the patient is found to have PD, PET-CT examination is required to confirm it, if progress is confirmed, it is recorded as PD, if progress cannot be confirmed, it may be false progression, and it is recorded as SD. If prostate cancer does not have biochemical recurrence, PET-CT examination is not required, and there is no metastasis by default, which is regarded as tumor control, and if biochemical recurrence occurs, it is regarded as tumor not controlled, and PET-CT is required to confirm tumor metastasis.

Note: Participants who aborted the trial for any reason (except loss to follow-up) before the end of the last radiation therapy were considered to have disease progression (PD) or were not controlled. Disease site evaluation uses the same approach as baseline, including consistent contrasted/non-contrast scans and prompt scanning. If changes are needed, the case must be discussed with a radiologist to determine whether an alternative approach is possible. If not, the objective situation in the future is unclear.

3.1.4.2 Secondary effectiveness evaluation indicators and their methods and timing of evaluation, recording, analysis

(1) Objective response rate (ORR).

Reason for selection: The Guidelines for the Review of Clinical Evaluation Technologies of Proton Carbon Ion Therapy Systems (CFDA Circular No. 4 [2018]) recommends the use of the latest version of the commonly used evaluation criteria for radiation oncology as the clinical trial evaluation criteria, so RECIST 1.1 is used Relevant indicators as effectiveness evaluation criteria; Due to the particularity of the disease, the evaluation method recommended in the relevant diagnosis and treatment guidelines is selected. All of them can directly measure the effect of radiotherapy and are widely recognized and applied by clinicians.

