Definition of indicators: CR or PR after the end of treatment is considered objective remission, prostate cancer has no biochemical recurrence at the end of the last treatment, and no regional lymph nodes or distant metastasis are considered objective remission. Proportion of participants who experienced objective remission at each time point after the end of the last treatment.

Metric type: Qualitative.

Data collection time: screening period, 1 month \pm 7 days, 3 months, \pm 7 days after the end of the last treatment.

Evaluation time: 1 month \pm 7 days, 3 months, \pm 7 days after the last treatment.

Site of evaluation: Tumor receiving radiation therapy.

Evaluation method: The changes in tumor CT or MRI imaging before and after treatment were evaluated by an independent imaging review panel according to RECIST 1.1. At 3 months of radiographic evaluation, if PD is found, PET-CT is required to confirm it.

Calculation formula: ORR = number of subjects in objective response / total number of subjects × 100%.

Criteria: See RECIST 1.1 for details. At the time of 3-month imaging evaluation, if the patient is found to have PD, PET-CT examination is required to confirm it, if progress is confirmed, it is recorded as PD, if progress cannot be confirmed, it may be false progression, and it is recorded as SD. If prostate cancer does not have biochemical recurrence, PET-CT examination is not required, and there is no metastasis by default, which is regarded as objective remission, and if biochemical recurrence occurs, it is regarded as not objectively remission, and PET-CT is required to confirm tumor metastasis.

Note: Participants who aborted the trial for any reason (other than loss to follow-up) before the end of the last radiotherapy were considered to have not responded objectively. Disease site evaluation uses the same approach as baseline, including consistent contrasted/non-contrast scans and prompt scanning. If changes are needed, the case must be discussed with a radiologist to determine whether an alternative approach is possible. If not, the objective situation in the future is unclear.

(2) Time to sustained remission (DOR).

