2.1 Effectiveness evaluation indicators

2.1.1 Key Effectiveness Indicators

• Tumor disease control rate (DCR) at 3 months after the end of last treatment

The occurrence of CR, PR and SD after the end of treatment was considered to be disease control, and the

absence of biochemical recurrence at the end of treatment of prostate cancer was considered to be disease control.

Proportion of subjects with disease control 3 months after the end of the last radiation therapy.

Calculation formula: DCR = number of subjects under disease control / total number of subjects \times 100%

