2.1.2 Secondary effectiveness measures

• Objective response rate (ORR)

CR or PR was considered objective remission at the end of treatment, no biochemical recurrence

occurred at the end of prostate cancer at the end of treatment, and no regional lymph node metastasis or

distant metastasis was considered objective remission. Proportion of subjects with objective remission at

each time point after the end of the last treatment.

Calculation formula: ORR = number of subjects with objective remission / total number of subjects ×

100%

Time to Sustained Remission (DOR)

The time from the first assessment of the tumor as CR or PR to the first assessment of PD or death

from any cause.

Calculation formula: DOR = time to first assessment of PD or death from any cause - time to first

Confidential Information Page 5 / 17

Statistical Analysis Plan Version: V1.0
Date: 2022-11-11

assessment of CR or PR.

• Tumor disease control rate (DCR) at 1 month after the end of last treatment

The occurrence of CR, PR and SD after the end of treatment was considered to be disease control, and

the absence of biochemical recurrence at the end of treatment of prostate cancer was considered to be disease

control. Proportion of subjects with disease control 1 month after the end of the last treatment.

Calculation formula: DCR = number of subjects under disease control / total number of subjects ×

100%

Tumor markers (if required)

Tumor marker examination was performed and clinically significant changes in tumor markers (before

and after radiation therapy) were reported at the discretion of the investigator.

• Tumor-specific symptoms

Symptoms are recorded according to the type of disease, which may include, but are not limited to, the

following: pain, swallowing function, mobility, bleeding, visual acuity, appetite/weight, superficial lymph

node size, and clinically significant changes in reported symptoms (before and after radiation therapy) as

judged by the investigator.

• Ease of use (ProBeam System, Radiation Therapy Management Software (OIS), Radiation

Therapy Planning Software (Eclipse))

Investigators using the corresponding functions scored according to the Likert scale and collected open-

ended questions to evaluate the comprehensive feeling of ease of use during the treatment.

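### SAP 5.4.1 makes the third reader's own value final whenever two readers differ, with no stated level of comparison, so one read can outvote two, mainly for ORR and 1-month DCR

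*SAP*

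**What the plan says.** The adjudication rule stands in SAP 5.4.1, under the primary endpoint. It starts from a comparison of two readers ("if the efficacy evaluation results of the two evaluators" agree, the shared result is kept). Otherwise, where the "two evaluations are inconsistent, the independent evaluation value of the third evaluator will be taken as the final" result, the third reader's value stands alone. The paragraph does not require the third value to match either of the first two, has no majority step, and does not define what counts as consistent. SAP 5.4.2 gives no separate rule for ORR or 1-month DCR.

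Protocol 3.1.4.1 describes what a reader produces: "The efficacy evaluation can be divided into complete response CR, partial response PR, disease stable SD, disease progression PD". Tumour changes "were evaluated by an independent imaging review panel according to RECIST 1.1".

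Both endpoints built on these reads are binary:
- DCR: "the occurrence of CR, PR and SD after the end of treatment is disease control" (SAP 2.1.1 agrees).
- ORR: "CR or PR after the end of treatment is considered objective remission" (SAP 2.1.2 agrees).

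Protocol 3.1.4.1 adds a safeguard. PD found at the 3-month imaging must be confirmed by PET-CT, and if it cannot be confirmed the subject is recorded as SD. Prostate cases without biochemical recurrence count as controlled without PET-CT.

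**The concern.** The reads have four levels and the endpoints have two. PR against SD is a disagreement on category but full agreement on disease control. CR against PR, and SD against PD, are disagreements on category but full agreement on response. If consistency is judged on category, such pairs go to a third reader whose single opinion then fixes an endpoint on which the first two had already agreed. If it is judged on the binary endpoint, this cannot happen. The SAP does not choose, so two programmers could derive different results from the same reads.

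At stake are the accuracy of ORR and 1-month DCR and, to a smaller extent, the power of the 3-month DCR.

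**Working it through.** **The plan's own figure.** With target 80%, expected value 95% (Protocol 3.1.2), two-sided 0.05 and power 80%:

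n = [1.96·√(0.80·0.20) + 0.8416·√(0.95·0.05)]² / 0.15² = (0.7840 + 0.1834)² / 0.0225 = 41.6, so 42.

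With 10% dropout, 42/0.9 = 46.7, so 47. Both stated sizes reproduce.

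**Slack in the success rule** (Clopper-Pearson lower limit above 80%):

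| n | Controlled | Lower limit | Result |
|---|---|---|---|
| 42 | 39 | 80.5% | pass |
| 42 | 38 | 77.4% | fail |
| 47 | 44 | 82.5% | pass |
| 47 | 43 | 79.6% | fail |

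At the boundary one subject changes the result, as it would for any single misclassification.

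**All reader triples.** Three readers and four categories give 4³ = 64 ordered triples. I count those in which the final result contradicts two of the three readers on the endpoint, assuming that every read falls in one of the four categories.

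| Endpoint | Category comparison | Binary comparison | Triples under category comparison (first two in either order) |
|---|---|---|---|
| DCR | 6 of 64 | 0 of 64 | CR/PR, CR/SD or PR/SD, then PD |
| ORR | 8 of 64 | 0 of 64 | CR/PR, then SD or PD; SD/PD, then CR or PR |

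For DCR the direction is fixed. Two readers who both say not controlled both say PD, so they agree and no third read is taken. For ORR both directions occur.

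**Size, by assumption.** Suppose each reader independently misses the true category by one step with probability e, split equally between the two neighbours (CR and PD have only one). An override then needs one true read, one error to one side and one to the other. Per subject with true category PR or SD the probability is

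2 · (e/2) · (1−e) · (e/2) = e²(1−e)/2,

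which is 0.0045, 0.0160 and 0.0315 at e = 10%, 20% and 30%. For DCR only true SD subjects contribute; for ORR true PR and true SD subjects both do. With true DCR 95%, two assumed mixes are:
- mix A: ORR 50% (PR 0.35, SD 0.45)
- mix B: ORR 20% (PR 0.15, SD 0.75)

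| Mix | e | DCR override | ORR override | Power at n=42, category vs binary |
|---|---|---|---|---|
| A | 10% | 0.45·0.0045 = 0.2% | 0.80·0.0045 = 0.4% | 81.1% vs 82.8% |
| A | 20% | 0.7% | 1.3% | 71.3% vs 78.0% |
| A | 30% | 1.4% | 2.5% | 55.7% vs 69.5% |
| B | 10% | 0.3% | 0.4% | 78.0% vs 81.0% |
| B | 20% | 1.2% | 1.4% | 58.5% vs 70.2% |
| B | 30% | 0.75·0.0315 = 2.4% | 0.90·0.0315 = 2.8% | 31.9% vs 51.8% |

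The DCR and power columns ignore PET-CT, so for the 3-month endpoint they are upper bounds on the harm. Without reader error the exact power at n=42 is 84.3%. The drop from there to the binary figure comes from reader error itself; only the gap within each pair is due to the adjudication rule. At e = 10%, ORR misclassification falls from about 1.0% to 0.6% when the comparison is binary.

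**Median as an alternative.** Order the categories CR, PR, SD, PD. The median of three reads lies on one side of a cut exactly when at least two reads do. The median therefore gives the 2-of-3 majority for DCR and ORR in all 64 triples, with a single category per assessment.

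**The case against.** Four arguments stand against the point.

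- **PET-CT covers the primary endpoint's weak spot.** A reader might infer that one minority PD read can by itself fail the trial at the boundary. The documents do not support that. The only possible DCR override is to PD, and at 3 months PD needs PET-CT confirmation or is recorded as SD. This stands. What remains is that SAP 5.4.1 does not mention PET-CT or say whether confirmation comes before or after the third read. The confirmation rule is written for the 3-month imaging, so it does not clearly cover 1-month DCR, and it does not address the boundary between response and SD.
- **The level of comparison is not stated.** A reader might infer that the SAP definitely compares categories. It does not say so, and on a binary reading there are no overrides. This stands too: the firm defect is an unspecified rule, with category comparison as the natural reading.
- **The DCR effect is conservative, and ORR carries no target.** Relative to a majority rule, the DCR override can only remove successes, so it cannot produce a false pass. ORR is secondary and has no target value, so its errors do not bear on pass or fail. Prostate cases without biochemical recurrence fall outside the rule for DCR. All of this stands and lowers the severity.
- **A purely binary rule can leave category and endpoint at odds.** With reads CR, PR, PD the subject would be a responder whose tabulated category is PD, and DOR needs one dated category per assessment. This is a fair objection to the binary version. The median version meets it.

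**Conclusion.** The point holds as a minor one. SAP 5.4.1 imposes the third reader's own value without a majority step and does not fix the level of comparison. On the natural reading one reader can override two for ORR in either direction, and for DCR only towards failure.

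The primary 3-month DCR is largely protected by PET-CT; any residual effect is lost power, not type I error inflation. The practical weight is on ORR and 1-month DCR.

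The size is an assumption, because no reader-discordance rate or expected response mix is given. Over the assumed range it is 0.4–2.8% of subjects for ORR. For DCR without PET-CT it is 0.2–2.4%, or about 0.1 (42·0.002) to 1.0 (42·0.024) subjects of 42. I also assume that the paragraph in 5.4.1 governs ORR and 1-month DCR, since 5.4.2 has no rule of its own.

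**What to change.** Revise the adjudication paragraph in SAP 5.4.1 and state that it also applies to the imaging endpoints in 5.4.2. Either version gives a 2-of-3 majority on both endpoints:

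1. **Median (preferred).** If the first two readers give the same category, it is final. If they differ, the final category is the median of the three reads in the order CR, PR, SD, PD. One coherent category then serves DCR, ORR and DOR.
2. **Binary.** Judge consistency separately on controlled yes/no for DCR and responder yes/no for ORR. The third reader decides only where that result differs. Say which category drives DOR.

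In both cases add that the protocol's PET-CT confirmation rule applies to the adjudicated 3-month result.

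The cost is one paragraph and a revised derivation, using the same readers and reads. The binary version also needs a footnote where the category table and the endpoint differ.
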